5.1.1 Risks Associated with Atezolizumab

Atezolizumab has been associated with risks such as the following: infusion-related reactions and immune-related hepatitis, pneumonitis, colitis, pancreatitis, diabetes mellitus, hypothyroidism, hyperthyroidism, adrenal insufficiency, hypophysitis, Guillain-Barré syndrome, myasthenic syndrome or myasthenia gravis, meningoencephalitis, and myocarditis.

Refer to the Atezolizumab Investigator's Brochure for a detailed description of anticipated safety risks for atezolizumab.

Systemic immune activation is a rare condition characterized by an excessive immune response. Given the mechanism of action of atezolizumab, systemic immune activation is considered a potential risk when given in combination with other immunomodulating agents. Systemic immune activation should be included in the differential diagnosis for patients who, in the absence of an alternative etiology, develop a sepsis-like syndrome after administration of atezolizumab.

The initial evaluation should include the following:

- CBC with peripheral smear
- PT, PTT, fibrinogen, and D-dimer
- Ferritin
- Triglycerides
- AST, ALT, and total bilirubin
- LDH
- Complete neurologic and abdominal examination (assess for hepatosplenomegaly)

If systemic immune activation is still suspected after the initial evaluation, contact the Medical Monitor for additional recommendations.

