5.2.3 Adverse Events of Special Interest (Immediately Reportable to the Sponsor)

Adverse events of special interest are required to be reported by the investigator to the Sponsor immediately (i.e., no more than 24 hours after learning of the event; see Section 5.3.5.4 for reporting instructions). Adverse events of special interest for this study include the following:

- Any of the following confirmed treatment-emergent autoimmune conditions:
 - Pneumonitis
 - Colitis
 - Endocrinopathies: diabetes mellitus, pancreatitis, or adrenal insufficiency or hyperthyroidism
 - Hepatitis
 - Transaminitis: Grade ≥ 2 (AST or ALT $>3 \times$ ULN and bilirubin $>2 \times$ ULN) OR AST or ALT $>10 \times$ ULN
 - Systemic lupus erythematosus
 - Neurologic: Guillain-Barré syndrome, myasthenia gravis, meningoencephalitis
 - Nephritis
- Events suggestive of hypersensitivity, cytokine release, influenza-like illness, systemic inflammatory response system, systemic immune activation, or infusion-reaction syndromes

- Cases of potential drug-induced liver injury that include an elevated ALT or AST in combination with either an elevated bilirubin or clinical jaundice, as defined by Hy's law (see Section 5.3.5.7)
- Suspected transmission of an infectious agent by the study drug, as defined below:
 - Any organism, virus, or infectious particle (e.g., prion protein transmitting transmissible spongiform encephalopathy), pathogenic or non-pathogenic, is considered an infectious agent. A transmission of an infectious agent may be suspected from clinical symptoms or laboratory findings that indicate an infection in a patient exposed to a medicinal product. This term applies only when a contamination of the study drug is suspected.

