5.3.1 Adverse Event Reporting Period

Investigators will seek information on adverse events at each patient contact. All adverse events, whether reported by the patient or noted by study personnel, will be recorded in the patient's medical record and on the Adverse Event eCRF.

After informed consent has been obtained **but prior to initiation of study drug**, only serious adverse events caused by a protocol-mandated intervention (e.g., invasive procedures such as biopsies, discontinuation of medications) should be reported (see Section 5.4.2 for instructions for reporting serious adverse events).

After initiation of study drug, all adverse events will be reported until 30 days after the last dose of study drug or until initiation of new anti-cancer therapy, whichever occurs first, and serious adverse events and adverse events of special interest will continue to be reported until 90 days after the last dose of study drug or until initiation of new anti-cancer therapy, whichever occurs first.

For patients participating in the optional long term follow-up (as outlined in Section 4.5.9) who continue to receive atezolizumab, all AE's will be reported until 30 days after the last dose of atezolizumab during this period of the study. Additionally, serious adverse events and non-serious adverse events of special interest will be reported until 90 days after the last dose of atezolizumab.

Female patients of childbearing potential will be instructed to immediately inform the investigator if they become pregnant during the optional long-term follow-up period or within 5 months after receiving their last dose of atezolizumab.

Pregnancies are to be reported to the Sponsor, as applicable, according to the same guidelines as outlined in Section 5.4.3.1.

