Diarrhea or colitis, Grade 4	
 • Permanently discontinue atezolizumab and contact Medical Monitor. ^c • Refer patient to GI specialist for evaluation and confirmation biopsy. • Initiate treatment with 1–2 mg/kg/day IV methylprednisolone or equivalent and convert to 1–2 mg/kg/day oral prednisone or equivalent upon improvement. • If event does not improve within 48 hours after initiating corticosteroids, consider adding an immunosuppressive agent. • If event resolves to Grade 1 or better, taper corticosteroids over ≥ 1 month.

GI = gastrointestinal.

- ^a Atezolizumab may be withheld for a longer period of time (i.e., > 12 weeks after event onset) to allow for corticosteroids (if initiated) to be reduced to ≤ 10 mg/day oral prednisone or equivalent. The acceptable length of the extended period of time must be agreed upon by the investigator and the Medical Monitor.
- ^b If corticosteroids have been initiated, they must be tapered over ≥ 1 month to ≤ 10 mg/day oral prednisone or equivalent before atezolizumab can be resumed.
- ^c Resumption of atezolizumab may be considered in patients who are deriving benefit and have fully recovered from the immune-related event. Patients can be re-challenged with atezolizumab only after approval has been documented by both the investigator (or an appropriate delegate) and the Medical Monitor.

ENDOCRINE EVENTS

Thyroid disorders, adrenal insufficiency, diabetes mellitus, and pituitary disorders have been associated with the administration of atezolizumab. Management guidelines for endocrine events are provided in [Table 4](#).

Patients with unexplained symptoms such as headache, fatigue, myalgias, impotence, constipation, or mental status changes should be investigated for the presence of thyroid, pituitary, or adrenal endocrinopathies. The patient should be referred to an endocrinologist if an endocrinopathy is suspected. Thyroid-stimulating hormone (TSH) and free triiodothyronine and thyroxine levels should be measured to determine whether thyroid abnormalities are present. Pituitary hormone levels and function tests (e.g., TSH, growth hormone, luteinizing hormone, follicle-stimulating hormone, testosterone, prolactin, adrenocorticotrophic hormone [ACTH] levels, and ACTH stimulation test) and magnetic resonance imaging (MRI) of the brain (with detailed pituitary sections) may help to differentiate primary pituitary insufficiency from primary adrenal insufficiency.

APPENDIX 8

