Immune-related myocarditis has been associated with the administration of atezolizumab. Immune-related myocarditis should be suspected in any patient presenting with signs or symptoms suggestive of myocarditis, including, but not limited to, dyspnea, chest pain, palpitations, fatigue, decreased exercise tolerance, or syncope. Immune-related myocarditis needs to be distinguished from myocarditis resulting from infection (commonly viral, e.g., in a patient who reports a recent history of GI illness), ischemic events, underlying arrhythmias, exacerbation of preexisting cardiac conditions, or progression of malignancy.

All patients with possible myocarditis should be urgently evaluated by performing cardiac enzyme assessment, an ECG, a chest X-ray, an echocardiogram, and a cardiac MRI as appropriate per institutional guidelines. A cardiologist should be consulted. An endomyocardial biopsy may be considered to enable a definitive diagnosis and appropriate treatment, if clinically indicated.

Patients with signs and symptoms of myocarditis, in the absence of an identified alternate etiology, should be treated according to the guidelines in [Table 6](#).

APPENDIX 8
Management of Atezolizumab-Specific Adverse Events (cont.)

Table 6 Management Guidelines for Immune-Related Myocarditis

Event	Management
Immune-related myocarditis, Grade 1	
 • Refer patient to cardiologist. • Initiate treatment as per institutional guidelines.
Immune-related myocarditis, Grade 2	
 • Withhold atezolizumab for up to 12 weeks after event onset^a and contact Medical Monitor. • Refer patient to cardiologist. • Initiate treatment as per institutional guidelines and consider antiarrhythmic drugs, temporary pacemaker, ECMO, or VAD as appropriate. • Consider treatment with 1–2 mg/kg/day IV methylprednisolone or equivalent and convert to 1–2 mg/kg/day oral prednisone or equivalent upon improvement.^a • If event resolves to Grade 1 or better, resume atezolizumab.^b • If event does not resolve to Grade 1 or better while withholding atezolizumab, permanently discontinue atezolizumab and contact Medical Monitor.^c

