4.6.2 Adverse Events

Verbatim description of adverse events (AEs) will be mapped to Medical Dictionary for Regulatory Activities (MedDRA) thesaurus terms and graded according to the NCI CTCAE v4.0. AEs will be summarized by NCI CTCAE grade. Multiple occurrences of the same event will be counted once at the maximum severity.

All AE data will be listed by study site, patient number, AE starting and ending study days, and study day of initiation of another non-protocol anti-cancer therapy after the last administration of study drug. SAEs and deaths data will also be listed.

All AEs occurring on the day of or after administration of the first dose of treatment will be summarized by thesaurus term, appropriate thesaurus levels, and NCI CTCAE v4.0 grade. Severe AEs (Grade ≥ 3), infusion related reactions, AEs relation to study drug, and AEs leading to study drug discontinuation or interruption will be summarized.

Serious adverse events (SAEs), AESIs, and adverse events leading to study drug discontinuation or interruption will be summarized separately.

Deaths and causes of death will be summarized.

Protocol Defined AE Reporting Period

After initiation of study drug, all AEs will be reported until 30 days after the last dose of study drug or until initiation of new anti-cancer therapy, whichever occurs first; SAEs and adverse events of special interest will continue to be reported until 90 days after the last dose of study drug or until initiation of new anticancer therapy, whichever occurs first. Any and treatment related SAEs and AESIs will be reported until study completion.

The above AEs reporting rules may be used to select AEs to be summarized if significant among of AEs are reported outside of the protocol defined AE reporting period.

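### The AESI list in Protocol 5.2.3 has no entry for myocarditis or hypophysitis, both of which 5.1.1 and Appendix 8 name as atezolizumab risks

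*Protocol*

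**What the plan says.** **Risks.** Protocol 5.1.1 lists the risks associated with atezolizumab. The list ends with "hypothyroidism, hyperthyroidism, adrenal insufficiency, hypophysitis, Guillain-Barré syndrome, myasthenic syndrome or myasthenia gravis, meningoencephalitis, and myocarditis". Appendix 8 repeats the association for the heart: "Immune-related myocarditis has been associated with the administration of atezolizumab". It does the same for the endocrine system: "Thyroid disorders, adrenal insufficiency, diabetes mellitus, and pituitary disorders have been associated with the administration of atezolizumab". Table 6 of that appendix covers myocarditis, and Table 4 has separate rows for hypophysitis.

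**AESI list.** Section 5.2.3 names particular confirmed autoimmune conditions. The endocrine line is "Endocrinopathies: diabetes mellitus, pancreatitis, or adrenal insufficiency or hyperthyroidism", and the neurologic line is "Neurologic: Guillain-Barré syndrome, myasthenia gravis, meningoencephalitis". The other conditions are pneumonitis, colitis, hepatitis, transaminitis, lupus and nephritis. Further bullets cover systemic reactions (hypersensitivity, cytokine release, systemic immune activation, infusion reactions), potential drug-induced liver injury, and suspected transmission of an infectious agent.

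**What AESI status controls.** Section 5.4 puts serious events, AESIs and pregnancies on the 24-hour list. Under 5.3.1, other adverse events are reported to 30 days after the last dose, whereas "serious adverse events and adverse events of special interest will continue to be reported until 90 days after the last dose of study drug". On study, both windows close early if new anti-cancer therapy starts. SAP 4.6 takes its special-interest events from the protocol, and SAP 4.6.2 adds: "Serious adverse events (SAEs), AESIs, and adverse events leading to study drug discontinuation or interruption will be summarized separately".

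**The concern.** The AESI list decides which non-serious events are reported quickly, followed into the late window and shown in their own summary. Immune-mediated toxicity can begin after dosing stops, which is presumably why the protocol keeps a longer window for AESIs. Two organ toxicities that the protocol itself attributes to the drug are not on the list. For those two, quick reporting and late collection depend on the investigator classing the case as serious. A reader of the AESI summary would also see no myocarditis or hypophysitis and could take that to mean none occurred. The stated safety objective is the incidence of adverse events, so a collection window that differs between named risks without explanation matters.

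**Working it through.** The plan gives no figure to reproduce here. The check compares lists and then traces the reporting rules.

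**Step 1: match 5.1.1 against 5.2.3.** Counting myasthenic syndrome or myasthenia gravis as one, 5.1.1 names 14 risks.

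- With an entry in 5.2.3 (11): infusion-related reactions, hepatitis, pneumonitis, colitis, pancreatitis, diabetes mellitus, hyperthyroidism, adrenal insufficiency, Guillain-Barré syndrome, myasthenia gravis, meningoencephalitis.
- With no entry (14 − 11 = 3): hypothyroidism, hypophysitis, myocarditis.

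**Step 2: could another bullet catch them?** The systemic immune activation bullet describes generalised reactions and would not capture isolated inflammation of the heart or pituitary. Hypophysitis recorded as adrenal insufficiency would be caught under that term. But 5.3.5.2 tells sites to record the diagnosis where it is known, and hypophysitis recorded as such is not caught.

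**Step 3: size of the collection gap.** For a non-serious case the window is 30 days as an ordinary adverse event and would be 90 days as an AESI. The gap is 90 − 30 = 60 days (days 31 to 90 after the last dose). This is a maximum, because on study both windows end at new anti-cancer therapy. It applies by date of onset: an event that began by day 30 is recorded and, under 5.5.1, followed until it resolves or is stable. After the windows close, 5.6 asks only for related serious events and AESIs, so it does not recover a late non-serious case.

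**Step 4: trace each type of case.**

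| Myocarditis or hypophysitis | 24-hour report | Collected | AESI summary | Other SAP tables |
|---|---|---|---|---|
| Non-serious, onset by day 30 | No | Yes | No | General tables; interruption or discontinuation table if drug is held or stopped |
| Non-serious, onset days 31–90 | No | No | No | None |
| Serious, onset by day 90 | Yes, as a serious event | Yes | No | General and serious-event tables; interruption or discontinuation table if it applies |

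**Step 5: is there another route to the sponsor?** Partly. Appendix 8 asks for Medical Monitor contact for myocarditis of Grade 2 or higher, and for hypophysitis that is Grade 4 or does not resolve (recurrent hypophysitis is handled as Grade 4). Non-serious Grade 1 myocarditis, and a first Grade 2 or 3 hypophysitis that resolves, carry no such instruction. Medical Monitor contact is not the formal 24-hour report and does not lengthen the collection window.

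**The case against.** Nothing in the documents requires 5.2.3 to mirror 5.1.1. Lupus and nephritis are AESIs without appearing in 5.1.1, so the lists may never have been meant to match. Seriousness is also broad: 5.2.2 includes hospitalisation and significant medical events. Myocarditis calls for urgent cardiac evaluation under Appendix 8, so many cases could be reported as serious. The non-serious, late-onset remainder is probably small. Medical Monitor contact gives a second route, and cases that interrupt drug enter a separate table.

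Most of this stands, and it limits the point. What it does not answer is why two named organ toxicities depend on the investigator's judgment of seriousness when eleven other named risks do not. The documents give no reason. The late non-serious case and the AESI summary remain uncovered.

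The documents do not support four stronger readings:

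- *That these cases are invisible, or that overall incidence is understated.* Events reported within their window are in the general tables, and nothing defines the AESI summary as the total of immune-mediated toxicity.
- *That nothing about a non-serious case is collected from day 31 to day 90.* Only cases with onset after day 30 are lost.
- *That the protocol treats both events as equally urgent.* The urgent-evaluation wording applies to myocarditis only.
- *That hypothyroidism is an equal error.* The endocrine line names hyperthyroidism and not hypothyroidism, which can be read as deliberate. Drug continues in asymptomatic cases, and patients with stable, treated autoimmune hypothyroidism may enrol.

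**Conclusion.** The point holds for myocarditis and hypophysitis, as a narrow misalignment in safety reporting. It has three effects: no 24-hour AESI report for non-serious cases; no collection of non-serious cases with onset after day 30, a gap of up to 60 days; and absence from the AESI summary at any seriousness. The third effect is a matter of presentation for any case already in the other tables.

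The conclusion assumes that sites and programmers apply the named terms in 5.2.3 as written. The lead-in wording is inclusive, but no passage adds further organ-specific conditions. The number of patients affected cannot be estimated, because the documents give no incidence for either event. No efficacy or biomarker analysis is touched. This is an inexpensive improvement, not a flaw that threatens the trial's conclusions.

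**What to change.** Reconcile 5.2.3 with 5.1.1 and Appendix 8:

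1. Add immune-related myocarditis and hypophysitis to the autoimmune conditions in 5.2.3. The 24-hour report and the 90-day window then follow from the existing text of 5.3.1, 5.4 and 5.4.2.2.
2. State in SAP 4.6.2 that the AESI summary uses the amended 5.2.3 list.
3. State whether leaving out hypothyroidism is intended.

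The cost is a short protocol amendment, an update to the eCRF completion guidance and a few extra expedited reports. No dose, treatment rule, test or visit changes. The SAP step can be taken alone for cases already in the database, but it would not recover late non-serious cases that were never collected.

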5.3 METHODS AND TIMING FOR CAPTURING AND ASSESSING SAFETY PARAMETERS

The investigator is responsible for ensuring that all adverse events (see Section 5.2.1 for definition) are recorded on the Adverse Event eCRF and reported to the Sponsor in accordance with instructions provided in this section and in Section 5.4, Section 5.5, and Section 5.6.

For each adverse event recorded on the Adverse Event eCRF, the investigator will make an assessment of seriousness (see Section 5.2.2 for seriousness criteria), severity (see Section 5.3.3), and causality (see Section 5.3.4).

5.3.1 Adverse Event Reporting Period

Investigators will seek information on adverse events at each patient contact. All adverse events, whether reported by the patient or noted by study personnel, will be recorded in the patient's medical record and on the Adverse Event eCRF.

After informed consent has been obtained **but prior to initiation of study drug**, only serious adverse events caused by a protocol-mandated intervention (e.g., invasive procedures such as biopsies, discontinuation of medications) should be reported (see Section 5.4.2 for instructions for reporting serious adverse events).

After initiation of study drug, all adverse events will be reported until 30 days after the last dose of study drug or until initiation of new anti-cancer therapy, whichever occurs first, and serious adverse events and adverse events of special interest will continue to be reported until 90 days after the last dose of study drug or until initiation of new anti-cancer therapy, whichever occurs first.

For patients participating in the optional long term follow-up (as outlined in Section 4.5.9) who continue to receive atezolizumab, all AE's will be reported until 30 days after the last dose of atezolizumab during this period of the study. Additionally, serious adverse events and non-serious adverse events of special interest will be reported until 90 days after the last dose of atezolizumab.

Female patients of childbearing potential will be instructed to immediately inform the investigator if they become pregnant during the optional long-term follow-up period or within 5 months after receiving their last dose of atezolizumab.

Pregnancies are to be reported to the Sponsor, as applicable, according to the same guidelines as outlined in Section 5.4.3.1.

5.3.2 Eliciting Adverse Event Information

A consistent methodology of non-directive questioning should be adopted for eliciting adverse event information at all patient evaluation timepoints. Examples of non-directive questions include the following:

"How have you felt since your last clinic visit?"

"Have you had any new or changed health problems since you were last here?"

5.3.3 Assessment of Severity of Adverse Events

The adverse event severity grading scale for NCI CTCAE v4.0 will be used for assessing adverse event severity. [Table 5](#) will be used for assessing severity for adverse events that are not specifically listed in the NCI CTCAE.

Table 5 Adverse Event Severity Grading Scale for Events Not Specifically Listed in the NCI CTCAE

Grade	Severity
1	Mild; asymptomatic or mild symptoms; clinical or diagnostic observations only; or intervention not indicated
2	Moderate; minimal, local, or non-invasive intervention indicated; or limiting age-appropriate instrumental activities of daily living ^a
3	Severe or medically significant, but not immediately life-threatening; hospitalization or prolongation of hospitalization indicated; disabling; or limiting self-care activities of daily living ^{b,c}
4	Life-threatening consequences or urgent intervention indicated ^d
5	Death related to adverse event ^d

NCI CTCAE = National Cancer Institute Common Terminology Criteria for Adverse Events.
 Note: Based on the most recent version of the NCI CTCAE (v 4.0), which can be found at: http://ctep.cancer.gov/protocolDevelopment/electronic_applications/ctc.htm

- ^a Instrumental activities of daily living refers to preparing meals, shopping for groceries or clothes, using the telephone, managing money, etc.
- ^b Examples of self-care activities of daily living include bathing, dressing and undressing, feeding oneself, using the toilet, and taking medications, as performed by patients who are not bedridden.
- ^c If an event is assessed as a "significant medical event," it must be reported as a serious adverse event (see Section 5.4.2 for reporting instructions), per the definition of serious adverse event in Section 5.2.2.
- ^d Grade 5 events must be reported as serious adverse events (see Section 5.4.2 for reporting instructions), per the definition of serious adverse event in Section 5.2.2.

